4. STUDY DESIGN

4.1. Overall Design

Main Study

This is a randomized, double-blind Phase 3 study to evaluate 6 dose levels of Ad26.COV2.S administered as a 2-dose schedule in healthy adults. In this main study, the safety, reactogenicity,

and immunogenicity of Ad26.COV2.S of 1 dose (dose 1 of the 2-dose regimen) and 2-doses of Ad26.COV2.S will be evaluated (Table 1). The lower dose (3.5×10^{10} vp, 2.5×10^{10} vp, and 1.25×10^{10} vp) levels mimic vaccine degradation to enable determination of product expiry. In order to increase the end of shelf-life specifications a potential target release titer of 7×10^{10} vp will be evaluated. A higher titer of 9×10^{10} vp will also be evaluated as is the upper limit of the release range (potential maximum vp at release). The study population will consist of healthy men and women aged between 18 and 55 years (inclusive), who have not previously received a vaccine against COVID-19 and have not had prior exposure to SARS-CoV-2 as assessed by local serology testing. Participants will receive Ad26.COV2.S administered IM.

A target of approximately, 1,350 participants in the main study (225 participants per active vaccine group [assuming approximately a 10.2% dropout]) will be randomized in parallel in a 1:1:1:1:1:1 ratio to 1 of 6 vaccination groups in this study. Participants will receive a 2-dose vaccination regimen at different dose levels (9×10^{10} vp, 7×10^{10} vp, 5×10^{10} vp, 3.5×10^{10} vp, 2.5×10^{10} vp, 1.25×10^{10} vp).

Table 1: Schematic Overview of Study Design and Groups for the Main Study

Group	N	Day 1 Vaccination 1	Day 57 Vaccination 2
1	For NI ~ 225	Ad26.COV2.S 9×10^{10} vp	Ad26.COV2.S 9×10^{10} vp
2	For NI ~ 225	Ad26.COV2.S 7×10^{10} vp	Ad26.COV2.S 7×10^{10} vp
3	For NI ~ 225	Ad26.COV2.S 5×10^{10} vp	Ad26.COV2.S 5×10^{10} vp
4	For NI ~ 225	Ad26.COV2.S 3.5×10^{10} vp	Ad26.COV2.S 3.5×10^{10} vp
5	For NI ~ 225	Ad26.COV2.S 2.5×10^{10} vp	Ad26.COV2.S 2.5×10^{10} vp
6	For NI ~ 225	Ad26.COV2.S 1.25×10^{10} vp	Ad26.COV2.S 1.25×10^{10} vp

Sub Study

An additional enrollment of adult participants 18 to 55 years, inclusive, will enroll into a sub study, into Groups 1, 3, 5 and 6 (Table 2) to further characterize the innate, pro-inflammatory and other relevant (eg, pro-thrombotic) responses to Ad26.COV2.S to better understand a possible risk to TTS events. Participants will receive Ad26.COV2.S administered IM.

A target of approximately 240 participants will be enrolled in the sub study and will receive a 2-dose vaccination regimen at either 9×10^{10} vp, 5×10^{10} vp, 2.5×10^{10} vp, or 1.25×10^{10} vp. This target may not be met due to the challenges of enrolling seronegative subjects into the study, so sub-study enrollment may stop at lower numbers.

Table 2: Schematic Overview of Study Design and Groups for the Sub Study

Group	N (Seronegative)*	N (Seropositive)	Day 1 Vaccination 1	Day 57 Vaccination 2
1	~ 40	~ 20	Ad26.COV2.S 9×10^{10} vp	Ad26.COV2.S 9×10^{10} vp
3	~ 40	~ 20	Ad26.COV2.S 5×10^{10} vp	Ad26.COV2.S 5×10^{10} vp
5	~ 40	~ 20	Ad26.COV2.S 2.5×10^{10} vp	Ad26.COV2.S 2.5×10^{10} vp
6	~ 40	~ 20	Ad26.COV2.S 1.25×10^{10} vp	Ad26.COV2.S 1.25×10^{10} vp

*Due to the challenges of enrolling seronegative subjects into the study, study enrollment may stop at lower numbers.

Table 3: Humoral Immunity Blood Sampling Schedule in Participants in All Groups of the Main and Sub Study

Groups**		Month 1	Month 2	Month 3	Month 6*	
	Day 1	Day 29	Day 57	Day 71		
1 6	●	●	●	●	●	

*post last vaccination

**Groups 1, 3, 5 and 6 in the sub study

Table 4: SARS-CoV-2 Non-S Serology Schedule in Participants in All Groups of the Main and Sub Study

Groups**		Month 1	Month 2	Month 3	Month 6*	
	Day 1	Day 29	Day 57	Day 71		
1 6		●		●		

*post last vaccination

** Groups 1, 3, 5 and 6 in the sub study

Table 5: Serum Sampling and PaxGene Schedule for Innate MoA in Participants in Groups 1, 3, 5 and 6 of the Sub Study

Groups	Day 1*	Day 2	Day 4	Day 8	Day 57*	Day 58	Day 60	Day 64
1, 3, 5 and 6	●	●	●	●	●	●	●	●

*pre vaccination

MoA=mechanism of Action

An IDMC has been commissioned for the Ad26.COV2.S program. Any significant safety information will be shared with the IDMC. Refer to Committees Structure in Section 10.3, for details.

A diagram of the study design is provided in Section 1.2, Schema.

Study Duration

The study duration from screening until the last follow-up visit will be at least 8 months per participant. The study will consist of a 28-day screening phase with vaccinations on Day 1 and Day 57, and a follow-up of at least 6 months after the last vaccination.

The vaccination phase consists of the administration of 1-dose of Ad26.COV2.S on Day 1 and 1-dose of Ad26.COV2.S on Day 57. A follow-up of at least 6 months after vaccination 2, is foreseen.

If a participant is unable to complete the study (post vaccination 1), but has not withdrawn consent, an early exit visit will be conducted, or the participant can continue with other study procedures. The end of study is considered as the last visit for the last participant in the study.

Study Procedures

For each group, safety will be assessed by collection of solicited local (at injection site) and systemic AEs, unsolicited AEs, MAAEs, AESIs, and SAEs. Other safety assessments include vital

signs measurements (heart rate, supine systolic and diastolic blood pressure, respiratory rate, and body temperature) and physical examinations at the time points indicated in Section 1.4.

After each vaccination, participants will remain under observation at the study site for at least 15 minutes for presence of any acute reactions and solicited events. Any solicited local or systemic AEs, unsolicited AEs, MAAEs, AESIs, SAEs, concomitant medications, and vital signs will be documented by study-site personnel following this observation period. In addition, participants will record solicited signs and symptoms in a diary for 7 days post vaccination.

The reporting periods of AEs, MAAEs, AESIs, and SAEs, and special reporting situations are detailed in Section 8.3. Reporting periods for concomitant therapy are outlined in Section 6.8. At each visit the participant will be asked if they have had a private/off-study COVID-19 test. If a participant receives a positive SARS-CoV-2 result from a private/off-study test (whether through PCR or serological testing)

- the participant can continue in the study for safety follow-up if they choose to:
 - This should be in accordance with local country and site level recommendations, including requirements for quarantine
 - They will not be permitted to receive further study vaccination administrations
 - The study staff will recommend the participant informs their medical care provider.
 - If there are no local country recommendations for COVID-19, the sponsor recommends the participant self-quarantines and does not come for a clinic visit until 2 consecutive negative PCR tests could be obtained.

In case the participant experiences signs or symptoms of COVID-19 after obtaining a positive SARS-CoV-2 test result, they should contact the study site at the time of symptom onset for recommendations on actions to follow for further care per local guidance.

See Section 8.3.1 on the reporting periods of this event.

A final safety follow-up visit is foreseen at least 6 months after the last vaccination for all participants.

From all participants, blood samples will be collected at selected timepoints indicated in Section 1.4, Schedule of Activities for humoral immunogenicity assessments, with an emphasis on neutralizing and binding antibody responses. Further details about the immunogenicity assessments are provided in Section 8.1.

An independent IDMC has been installed for the different studies throughout the COVID-19 vaccine program. Refer to Section 10.3.6 for details.

The planned primary and final analyses are detailed in Section 9.5.

A diagram of the study design is provided in Section [1.2](#).

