10.2 Appendix 2: Clinical Laboratory Tests		
1.1 Synopsis 4.1 Overall Design	Study duration has been changed from 13-15 months to at least 8 months and follow up changed from 12 to 6 months.	Due to the reduction of follow up from 12 to 6 months.
1.2 Schema for Participants in the Main Study 1.3 Schema for Participants in the Sub Study 1.4.1 2-dose Vaccination Schedule for Participants in the Main Study 1.4.2 2-dose Vaccination Schedule for the Sub Study Participants	Given the follow up period has been reduced to 6 months, there are some participants in the study who would have already had their 6-month visit. For those participants, a final phone call for safety follow up has been added.	To capture any additional safety information from participants who already had been in the study beyond 6 months post vaccination.
1.1 Synopsis 9.1 Statistical Hypotheses	Text has been added explaining the change in the sequential order of non-inferiority testing.	The 2.5×10^{10} vp dose will be tested before the 7×10^{10} vp in the sequential testing due to an increased risk to fail non-inferiority as a consequence of a smaller sample size in the 7×10^{10} vp group.
1.1 Synopsis 9.2 Sample Size Determination	Added the expected power based on % of dropout due to various reasons (eg, lost to follow-up, participants with major protocol deviations with impact on immunogenicity, participants who become N-seropositive during the study or with a confirmed SARS-CoV-2 infection, and participants who received their vaccination outside the allowed window). Also, an explanation for the possible addition of the sub study participants in the primary analysis has been added.	The power calculations show why the sub study participants need to be added to the main study primary analysis for non-inferiority.
1.1 Synopsis 6.3 Measures to Minimize Bias: Randomization and Blinding 9.5 Planned Analyses	Text has been added stating results from the main and sub study may be reported together rather than in separate reports.	Clarification that the results from the main and sub study may be available at the same time.
1.1 Synopsis 2.1 Study Rationale 3 OBJECTIVES AND ENDPOINTS 9.1 Statistical Hypotheses 9.2 Sample Size Determination 9.2.1 Immunogenicity 9.4.2 Primary Endpoint(s)	The order of the sequential hypothesis testing has been modified.	To reduce the increased risk to fail non-inferiority as a consequence of a smaller sample size in the 7×10^{10} vp group.

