A target of approximately 240 participants will be enrolled in the sub study and will receive a 2-dose vaccination regimen at either 9×10^{10} vp, 5×10^{10} vp, 2.5×10^{10} vp, or 1.25×10^{10} vp. This target may not be met due to the challenges of enrolling seronegative subjects into the study, so sub-study enrollment may stop at lower numbers.

Table: Schematic Overview of Study Design and Groups for the Sub Study

Group	N (Seronegative)*	N (Seropositive)	Day 1 Vaccination 1	Day 57 Vaccination 2
1	~ 40	~ 20	Ad26.COV2.S 9×10^{10} vp	Ad26.COV2.S 9×10^{10} vp
3	~ 40	~ 20	Ad26.COV2.S 5×10^{10} vp	Ad26.COV2.S 5×10^{10} vp
5	~ 40	~ 20	Ad26.COV2.S 2.5×10^{10} vp	Ad26.COV2.S 2.5×10^{10} vp
6	~ 40	~ 20	Ad26.COV2.S 1.25×10^{10} vp	Ad26.COV2.S 1.25×10^{10} vp

*Due to the challenges of enrolling seronegative subjects into the study, study enrollment may stop at lower numbers.

An IDMC has been commissioned for the Ad26.COV2.S program. Any significant safety information will be shared with the IDMC.

The study duration from screening until the last follow-up visit will be at least 8 months per participant. The study will consist of a 28-day screening phase with vaccinations on Day 1 and Day 57, and a follow-up through at least 6 months after the last vaccination.

End of Study Definition

The end of study is considered as the last visit for the last participant in the study.

NUMBER OF PARTICIPANTS

Overall, a target of approximately 1,350 adult participants aged 18 to 55 years, inclusive, will be enrolled in the main study. A total of a target of approximately 240 participants 18 to 55 years, inclusive, will be enrolled in the sub study.

DOSAGE AND ADMINISTRATION

Participants will be vaccinated at the study site according to the schedule detailed above:

- Ad26.COV2.S will be supplied at a concentration of 2×10^{11} vp/mL as a suspension in single-use vials, with an extractable volume of 0.5 mL. Formulation buffer of Ad26.COV2.S will be supplied as diluent. Dose levels throughout the different groups will be 9×10^{10} vp, 7×10^{10} vp, 5×10^{10} vp, 3.5×10^{10} vp, 2.5×10^{10} vp and 1.25×10^{10} vp.

A volume of 0.5 mL will be administered to all participants.

IMMUNOGENICITY EVALUATIONS

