1.4. Schedule of Activities (SoA)

1.4.1. 2-dose Vaccination Schedule for Participants in the Main Study

Phase	Screening ^a	Study Period ^b										
		1	2	Phone Call ^c	3	4	Phone Call ^c	5	Phone Call ^c	6	Phone Call ^d	Exit ^e
Clinic Visit #												
Visit Timing		Vac 1	Post Vac 1 + 7 d	Post Vac 1 + 28 d	Vac 2	Post Vac 2 + 7 d	Post Vac 2 + 14 d	Post Vac 2 + 28 d	Post Vac 2 + 24 w			
Visit Day/Week	-28 to 1	Day 1	Day 8	Day 29	Day 57	Day 64*	Day 71*	Day 85*	Week 32* (6m post Vac 2)			
Visit Window			±2 d	±3 d	-3/+7 d	±2 d	±3 d	±3 d	±21 d	+1 month		
Visit Type	Screening	Vaccine 1	Safety	Safety and Immuno	Vaccine 2	Safety	Safety and Immuno	Safety	Safety and Immuno	Safety		
Written informed consent ^f	●											
Inclusion/exclusion criteria	●	● ¹										
Demographics	●											
Medical history/prestudy meds	●											
Physical examination ^g	●											
Vital signs ^h incl. body temperature	●	● ²			● ²							
Nasal swab sample and test for SARS CoV 2 RNA	● ⁶	● ⁷										
Serological test for anti SARS CoV 2 antibody (Local Laboratory) ⁱ	● ⁶ [2 mL]											
Randomization		● ¹										
Prevaccination check ^j		● ¹			● ¹							
Urine pregnancy test ^k	●	● ¹			● ¹							
Humoral Immunity (serum), blood draw, mL ^l		● ¹ 10		● 12	● ¹ 10		● 10		● 10		● ³ 10	
Clinical lab blood draw (whole blood, plasma, serum), mL ^m		● ¹ 15		● 15	● ¹ 15		● 15					
SARS CoV 2 N Serology, mL (Central Laboratory) ⁿ				● 2.5			● 2.5					
Vaccination		●			●							
15 minutes post vaccination observation ^o		●			●							

Phase	Screening ^a	Study Period ^b												
		1	2	Phone Call ^c	3	4	Phone Call ^c	5	Phone Call ^c	6	Phone Call ^d	Exit ^e		
Clinic Visit #	1													
Visit Timing		Vac 1	Post Vac 1 + 7 d	Post Vac 1 + 28 d	Vac 2	Post Vac 2 + 7 d	Post Vac 2 +14 d	Post Vac 2 + 28 d	Post Vac 2 + 24 w					
Visit Day/Week	-28 to 1	Day 1	Day 8	Day 29	Day 57	Day 64*	Day 71*	Day 85*	Week 32* (6m post Vac 2)					
Visit Window			±2 d	±3 d	-3/+7 d	±2 d	±3 d	±3 d	±21 d	+1 month				
Visit Type	Screening	Vaccine 1	Safety	Safety and Immuno	Vaccine 2	Safety	Safety and Immuno	Safety	Safety and Immuno	Safety				
Solicited AE recording		- Continuous-			- Continuous-						● ⁴			
Unsolicited AE recording ^g		----- Continuous through +28 d -----			----- Continuous through +28 d -----						● ⁵			
SAE/AESI recording ^h		----- Continuous -----									●			
COVID 19 recording ⁱ		----- Continuous -----									●			
MAAE recording ^j		----- Continuous -----									●			

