Concomitant meds ^k		----- Continuous -----									●			
Participant diary distribution ^l		●			●									
Participant diary review ^m			●			●								
Approx. blood draw per day, mL:	2	25		29.5	25		27.5		10		10			
Approx. cumulative blood draw, mL:	2	27		56.5	81.5		109		119					

●¹ pre vaccination; ●² pre and post vaccination; ●³ blood samples for immunogenicity will only be taken if the early exit visit is at least 10 days after the previous immunogenicity blood draw; ●⁴ if within 7 days of the previous vaccination; ●⁵ if within 28 days of the last vaccination; ●⁶ Screening diagnostic test for SARS CoV 2 past or current infection will be performed. Valid results taken within 28 days will also be acceptable; ●⁷ to be repeated pre vaccination if the screening test was done more than 4 days before Day 1

*The phone call or these visits (including their window) are to be scheduled relative to the actual day of the previous vaccination, indicated as Visit Timing days/weeks post Vac 2.

- Screening will be performed within 28 days prior to the first study vaccination or on the day of vaccination. If screening is performed on the day of vaccination, Visit 1 and Visit 2 will coincide on Day 1. Screening must be completed, and all eligibility criteria must be fulfilled prior to randomization and vaccination.
- If a participant shows COVID-19 like symptoms, the participant should contact the site for guidance and must follow their local country and site level recommendations for COVID-19.

- c. The site will contact the participant 7 days post vaccination 1, 7-days post vaccination 2, and 28 days post vaccination 2 to enquire about compliance of patient diary completion that occurred between the actual vaccination visit and the current day.
- d. Within 1 month, the site will contact any participants who have already had their 6-month post Vac 2 visit (Visit 6) but have not yet reached 12-months post Vac 2 for additional safety follow up.

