5.1.2. Phase Definitions

The phases in the study will be constructed, as follows in [Table 5](#)

Table 5: Phase Definitions

Phase	Phase #	Period	Period #	Interval	
				From	To
Screening	1			Date and time of signing the informed consent form	One minute prior to start of post dose 1 period
Post-dose	2	Post-dose 1	1	Date and time of first vaccination	Minimum of: a) 23:59 at the date of last contact (for early discontinuation) b) One minute prior to the date of unblinding visit or database cut-off date, whichever occurs first c) 23:59 on 28 days after the first vaccination (23:59 of day of vaccination + 28 days)
Follow-up 1	3			One minute after post-dose 1 period end	Minimum of: a) 23:59 at the date of last contact (for early discontinuation) b) One minute prior to the date of unblinding visit or database cut-off date, whichever occurs first c) One minute prior to date and time of second vaccination
Post-dose	2	Post-dose 2	2	Date and time of second vaccination	Minimum of: a) 23:59 at the date of last contact (for early discontinuation) b) One minute prior to the date of unblinding visit or database cut-off date, whichever occurs first c) 23:59 28 days after the second vaccination (23:59 of day of vaccination + 28 days)
Follow-up 2	4			One minute after post-dose 2 period end	Minimum of: a) 23:59 at the date of last contact (for early discontinuation) b) One minute prior to the date of unblinding visit or database cut-off date whichever occurs first

					c) One minute prior to 6 months after second vaccination
Follow-up 3	5			One minute after post-dose 2 period end	
Minimum of:
 
a) 23:59 at the date of last contact (for early discontinuation)
 
b) One minute prior to the date of unblinding visit or database cut-off date, whichever occurs first
 
c) 23:59 at the date of last visit

Note: the end of regimen phase should be the end of the last post dose period

FU3: Full follow-up from end of post dose 2 to end of study or last contact

Post-dose 1 and post dose 2 Combined includes events occurring in the post-dose 1 and/or post dose 2 phases (not including FU 1 or FU2 or FU3)

For final analysis the following criteria for Follow-Up 3 will be used 23:59 at date of last contact (for early discontinuation or date of last visit)

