5.3.3.2. Missing Data

Missing data will not be imputed. Participants who do not report an event/concomitant medication will be considered as participants without an event/concomitant medication. An AE with a missing severity or relationship will be considered as an AE reported but will be considered as not reported for the severity or relationship. For example, an AE with missing severity will be considered as an AE reported for the analysis of any grade but will be considered as not reported for the analysis of at least grade 3.

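### For participants who reach Week 32 under Amendment 7, the schedule does not guarantee the stated minimum follow-up or 6-month MAAE capture, and SAP Follow-up 2 can run past the last contact

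*Protocol*

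**What the plan says.** Protocol Section 4.1 gives a minimum follow-up twice. Under Study Duration: "A follow-up of at least 6 months after vaccination 2, is foreseen". Under Study Procedures: "A final safety follow-up visit is foreseen at least 6 months after the last vaccination for all participants". The Synopsis and Section 4.1 add a total duration: "The study duration from screening until the last follow-up visit will be at least 8 months per participant".

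The schedules (Sections 1.4.1 and 1.4.2) put the last clinic visit 24 weeks after dose 2, window ±21 days, under the label "Week 32* (6m post Vac 2". A safety phone call follows in the table, and footnote d limits who receives it: "Within 1 month, the site will contact any participants who have already had their 6-month post Vac 2 visit (Visit 6", provided they have not yet reached 12 months. The Amendment 7 summary of changes explains that some participants would already have passed their 6-month visit when follow-up was shortened: "For those participants, a final phone call for safety follow up has been added". Section 4.4 defines completion by attendance at the 6-month visit, not by elapsed time.

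MAAEs are a secondary safety endpoint to 6 months after dose 2 (Protocol Section 3). Footnote s of both schedules starts their reporting at the first vaccination.

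In SAP Table 5 (Section 5.1.2), Follow-up 2 ends at the earliest of three times: last contact, for early discontinuation only; unblinding or database cut-off; and "One minute prior to 6 months after second vaccination". Follow-up 3 has a different third item, the date of the last visit. SAP Section 5.2 tabulates median follow-up duration per phase.

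**The concern.** A stated minimum should hold for every participant who follows the schedule. Here, a participant can attend inside the permitted window, count as a completer, and still be last contacted before 6 months. While follow-up ran to 12 months, the 24-week visit was not the end of observation and a later contact could pick up events after it. Amendment 7 made that visit the last scheduled contact for participants who had not yet reached it.

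Two reported items are affected. The MAAE endpoint is labelled as running to 6 months after dose 2, yet events between the last visit and that date have no scheduled ascertainment in these participants. And because Follow-up 2 has no last-visit rule for completers, the phase can extend beyond the last contact, which lengthens its tabulated duration.

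**Working it through.** **Inputs.** Dose 2 on Day 57, 56 days after dose 1, window −3/+7 days; last visit 24 weeks after dose 2, ±21 days; screening from 28 days before dose 1 up to the same day (all Protocol Section 1.4). The post-dose 2 period ends 28 days after dose 2 (SAP Table 5). Neither document defines a month in days, so two readings are carried: calendar months (6 months = 181 to 184 days, mean 182.6) and 28-day months (6 months = 168 days).

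**The plan's own label.** 24 × 7 = 168 days; 56 + 168 = 224 days = 32 weeks. The Week 32 label reproduces.

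**Last visit after dose 2.** Earliest 168 − 21 = day 147; nominal day 168; latest 168 + 21 = day 189.

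| Last visit | Short of 182.6 days | Short of 168 days |
|---|---|---|
| Day 147 | 35.6 (range 34 to 37) | 21 |
| Day 168 | 14.6 (range 13 to 16) | 0 |
| Day 189 | none | none |

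The ranges use 181 and 184 days. On calendar months only the last 6 to 9 days of the 43-day window reach 6 months.

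**Share of the MAAE window.** The window starts at dose 1, so on calendar months its length is 56 + 182.6 = 238.6 days. Nominal visit: 14.6 / 238.6 = 6%. Earliest visit: 35.6 / 238.6 = 15%. On the 168-day reading the window is 56 + 168 = 224 days and the earliest visit leaves 21 / 224 = 9% without a scheduled contact.

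**Total duration from screening.**
- Same-day screening, nominal visits: 0 + 56 + 168 = 224 days, 7.4 calendar months, or exactly 8 months of 28 days.
- Same-day screening, dose 2 three days early, earliest last visit: 0 + 53 + 147 = 200 days, 6.6 calendar months. This is also below 224 days.
- Full 28-day screening, nominal visits: 28 + 56 + 168 = 252 days, 8.3 calendar months.

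**Follow-up 2 for a completer, with no earlier unblinding or cut-off.** Observed length = last visit − 28; credited length = 6 months − 28.

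| Last visit | Observed | Credited (calendar) | Excess | Credited (168 days) | Excess |
|---|---|---|---|---|---|
| Day 147 | 119 | 154.6 | 35.6 (30%) | 140 | 21 (18%) |
| Day 168 | 140 | 154.6 | 14.6 (10%) | 140 | 0 |

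For a visit at or after 6 months the excess is zero.

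**The case against.** The protocol itself treats 24 weeks as 6 months. The visit label says so, and Section 4.1 Tables 3 and 4 place Day 29 at Month 1 and Day 57 at Month 2, which fits 28-day months. On that convention an on-time visit has no shortfall, and 224 days is exactly 8 months. This stands: the nominal gap depends on an undefined unit. It does not remove the 21-day gap at the early end of the window, nor the 200-day course.

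Section 8 asks participants to attend on the exact planned day and to use the window only if absolutely necessary, so the earliest case should be uncommon. Participants already past Visit 6 at Amendment 7 have an extra safety call, and some had already reached 1 year. This stands too, and the documents do not say how many participants remain affected.

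A reader might infer that the 6-month follow-up and the MAAE endpoint fail outright. They do not: visits late in the window reach 6 calendar months, so the right term is not guaranteed.

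A reader might also infer that Table 5, with the rule in SAP Section 5.3.3.2 ("Participants who do not report an event/concomitant medication will be considered as participants without an event/concomitant medication"), biases MAAE proportions downward. The documents do not support that. SAP Section 5.3.3 reports numbers and percentages of participants with an event, Section 5.3.3.1 allocates events by start date, and no person-time rate is specified. Ending Follow-up 2 earlier would change neither numerator nor denominator. Any missed late MAAE comes from the visit schedule, not from the phase rule. The visit timing is the same for all randomised dose groups, safety is descriptive, and the non-inferiority analysis uses Days 29 and 71.

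**Conclusion.** The point holds in a limited form. For participants who reach Week 32 under Amendment 7, the schedule guarantees neither 6 months after dose 2, nor scheduled MAAE capture to 6 months, nor 8 months in total. The shortfall after dose 2 is about 15 days at the nominal visit and 36 at the earliest on calendar months, or 0 and 21 days if 6 months is 168 days. Separately, the Follow-up 2 rule credits a completer seen before 6 months with unobserved time, up to about 30% of the observed phase on calendar months and 18% on the 168-day reading. The effect is confined to follow-up duration for that phase, since Follow-up 3 already ends at the last visit.

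This assumes that footnote d means participants past Visit 6 when Amendment 7 took effect, as the summary of changes indicates, and that a completer's Follow-up 2 is not cut earlier by unblinding or database cut-off. No between-dose bias and no effect on the primary analysis is shown. The case for acting is that a study report would otherwise repeat a minimum follow-up and a phase length that the schedule does not support.

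**What to change.** 1. In SAP Table 5, end Follow-up 2 at the earliest of 6 months after dose 2, unblinding or database cut-off, and 23:59 on the date of last visit or contact for all participants, as Follow-up 3 effectively does.
2. Define 6 months in days in both documents.
3. Reconcile the Synopsis, Section 4.1 and both schedules in one of two ways. Either restate the follow-up, study duration and MAAE period as running to the Week 32 visit (24 weeks ± 21 days after dose 2), or extend the existing safety call to participants whose Week 32 visit falls before 6 months.

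The first two changes, and the first option of the third, cost only wording, with a slightly shorter stated follow-up. The second option costs one phone call for each participant seen early.
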